### 3. ABBREVIATIONS

AE	Adverse event
AR	Adverse reaction

CI	Chief Investigator
CRA	Clinical Research Associate (Monitor)
CRF	Case Report Form
CRO	Contract Research Organisation
CT	Clinical Trials
CTRG	Clinical Trials and Research Governance
DMC/DMSC	Data Monitoring Committee / Data Monitoring and Safety Committee
ERC	Early rectal cancer
GCP	Good Clinical Practice
GP	General Practitioner
IB	Investigators Brochure
ICF	Informed Consent Form
ICG	Indocyanine green
ICH	International Conference of Harmonisation
IMP	Investigational Medicinal Product
IRB	Independent Review Board
MDT	Multi-disciplinary team
MHRA	Medicines and Healthcare products Regulatory Agency
NHS	National Health Service
NIR	Near infrared
NRES	National Research Ethics Service
OXTREC	Oxford Tropical Research Ethics Committee
PI	Principal Investigator
PIL	Participant/ Patient Information Leaflet
R&D	NHS Trust R&D Department
REC	Research Ethics Committee
SAE	Serious Adverse Event
SAR	Serious Adverse Reaction
SDV	Source Data Verification
SNLB	Sentinel lymph node biopsy
SOP	Standard Operating Procedure
SPIO	Superparamagnetic iron oxide particles
SUSAR	Suspected Unexpected Serious Adverse Reactions
TEM	Transanal endoscopic microsurgery

TME	Total mesorectal excision
TMF	Trial Master File
TSG	Oxford University Hospitals Trust / University of Oxford Trials Safety Group

#### 4. BACKGROUND AND RATIONALE

The scientific rationale mainly comes from studies involving sentinel lymph node biopsy (SLNB) in breast cancer (Krag et al, 2010). No difference was seen in overall survival or disease free survival when women had SLNB compared to women who had SLNB and axillary node dissection (AND) in women with disease negative sentinel nodes. A further study in breast cancer patients with positive SLNB but no clinical evidence of lymph node involvement demonstrated that there was no difference in outcome when comparing those who had no further axillary surgery versus those who had subsequent completion axillary lymph node dissection (Giuliano et al, 2011). In both studies, a high proportion of patients were treated with adjuvant systemic chemotherapy and external beam radiation. These data strongly support the need for further research into the role of organ-preservation surgery in other cancer types.

Sentinel node interrogation has yet to be fully evaluated in rectal cancer surgery due to technical limitations of obtaining SLNB from the mesorectum. As for breast cancer, rectal cancers can be excised by either radical or organ-preservation surgical techniques. Decision for either method is currently based on the risk of local recurrence or presence of lymph node metastasis. Radical surgery involves removal of the whole of the mesorectum and is associated with significantly worse functional outcome, morbidity and mortality. Current guidelines recommend that full thickness removal of the rectal tumour by transanal endoscopic microsurgery, TEM, is appropriate for small T1N0 cancers (less than 3 cm) where the risk of local recurrence (LR) is relatively low (NCCN guidelines, 2014). This surgery avoids removal of the whole mesorectum. The risk of LR increases with the depth of penetration of the rectal wall. Results from the UK TEM database show that the risk of LR at 36 months trebles when comparing T1N0 to T2N0 cancers of the same diameter (4.4% versus 14.3% respectively) (Bach et al, 2009). However, in 85% of rectal cancers that are T2N0 (based on tumours that are 2.1-3 cm diameter, with no lymphatic invasion) there is no LR at 36 months. There is a risk of subjecting patients to over-treatment in terms of surgery resulting in a significant risk of morbidity, mortality and impaired quality of life. On the other hand under-treatment of some “high risk” cancers would lead to recurrence. SLNB at TEM would potentially allow clinicians to excise T2 cancers in order to further stratify cancers based on future risk. This would avoid surgical over-treatment and under-treatment.

Our research objective will be to assess the feasibility of using a magnetic non-radioactive iron-based tracer (Sienna+ or Magtrace) and a handheld magnetometer (SentiMag) to accurately define the position of sentinel lymph nodes in patients with operable rectal cancer. This technology has already been successfully used in breast cancer patients in a UK multi-centre trial (Thill et al, 2014). The tracer is non-radioactive and safe (there is an extremely low risk of a hypersensitivity reaction to iron-based compounds, magnetic tracer and superparamagnetic iron oxide (SPIOs)). Our research will be done in two stages. The first “ex-vivo” stage will involve mapping tracer activity in total mesorectal specimens from rectal cancer patients. These will be focused on patients with rectal cancers where standard radical surgery is recommended. In this group we will also inject indocyanine green dye (ICG) into the tumour during surgery to act as an adjunct to identifying the lymph nodes while we develop confidence with the SentiMag system. ICG is a widely-used dye with many applications in medicine, including SLN

identification, and has been used with some positive early results in rectal cancer (Cahill et al, 2012). The second stage would then involve an “in-vivo” study in patients with early rectal cancers (ERCs) that are suitable for TEM. We would use SentiMag technology to assess the feasibility and safety of SLNB in patients with ERC by taking lymph nodes with "peaks" of tracer activity from the mesorectum. After completion of this study, our intention will be to perform a clinical trial based on SLNB in rectal cancer patients.

There are no major ethical or legal issues associated with this study as SLNB is established in breast cancer practice. Our research will help to further define suitability for either localised or radical surgery in early rectal cancer patients.

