Secondary	
[A] Correlate histopathology findings with tracer uptake in the lymph nodes.
 
[B] Radiologically evaluate the drainage pattern of Sienna+ tracer using a high resolution MRI, to establish a baseline for individual variation.
 
EX-VIVO part of study:
 
[C] Measure the distribution and spread of the Sienna+ tracer using the SentiMag hand-held probe in mesorectal specimen after rectal cancer surgery (in the pathology department). This is to establish a baseline in individual variation between specimens.
 
[D] Assess the accuracy of the SentiMag hand-held probe/Sienna+ tracer in identifying "sentinel" lymph nodes. This will be determined in conjunction with a pathologist who will systematically identify lymph nodes in the standard manner. The level of tracer activity in each lymph node will be measured and correlated with position and tumour cell involvement.
 
IN-VIVO part of study:
 
[E] Establish feasibility of sentinel lymph node biopsy during localised surgery for early rectal cancer using SentiMag hand-held probe to identify "peaks" of tracer activity intro-operatively.
	
[A] Correlation between histopathology findings and tracer uptake (determined by Sentimag probe) in the lymph nodes.
 
[B] High-resolution MRI mapping of the drainage pattern of Sienna+ tracer.
 
EX-VIVO part of the study:
 
[C] Mapping of the distribution of Sienna+ tracer in the mesorectal specimen using the SentiMag hand-held probe after rectal cancer surgery.
 
[D] Accuracy of the SentiMag hand-held probe/Sienna+ tracer in identifying "sentinel" lymph nodes, determined by correlation with histopathology findings.
 
IN-VIVO part of study:
 
[E] Number of TEM operations where the "sentinel" lymph node could be identified during surgery using the Sentimag probe, and then successfully removed.

Device name	Magtrace® tracer and SentiMag® magnetometer	
Device Manufacturer	Endomagnetics, Cambridge	
Device Classification	Class IIa device	

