## **8. TRIAL PROCEDURES**

Methodology training for investigators: At the start of the study, the principal investigators will undergo methodology training and practice the use of the hand held SentiMag probe device. The chief investigator will standardize the sentinel lymph node biopsy technique during this feasibility study.

Screening and preliminary discussion of research project with potential participant: During the standard pre-operative clinic visit patients who have been identified as potential participants will be screened and informed about the study by a clinician or colorectal specialist nurse. They will have an opportunity to ask questions and will be provided with an information sheet.

Informed consent: In the endoscopy unit a clinician will discuss the study further and take consent if the patient is willing to proceed. A letter will be sent to the participant's GP informing them of the study.

Endoscopic injection of tracer and post-injection monitoring: The magnetic tracer will be injected approximately 5 days before surgery during endoscopic assessment of the tumour. The rectal tumour

will be visualized by endoscopy, as per standard clinical practice. Up to 2ml tracer solution will be infiltrated systematically (in 4 quadrants) into the submucosa around the rectal tumour. After the procedure, patients will be monitored for 1 hour to ensure no hypersensitivity or adverse reactions occur and provided with a contact telephone number in case of any delayed reaction or side-effects on discharge.

MRI scan of pelvis: On the same day as the endoscopy unit visit or the day of surgery, patients will undergo an MRI scan of the pelvis. This will be done 2-3 hours after the endoscopic injection of tracer or on the day of surgery.

Rectal cancer surgery: Patients will undergo rectal cancer surgery according to their clinical indication. During surgery for the “ex-vivo” group, indocyanine green dye (ICG) will be injected near the tumour. At the conclusion of surgery the surgeon will make an assessment as to whether the tracer injection affected surgery, for example by causing inflammation in the tissue planes.

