Intra-operative detection of the sentinel lymph node using the SentiMag probe and excision of the identified node (second part participants only): During rectal cancer surgery, following excision of the tumour, the surgeon will use the hand held SentiMag probe to identify the sentinel lymph node. This will then be dissected and removed for subsequent histological analysis.

Post-operative monitoring: Following surgery patients will be admitted to the colorectal ward for routine post-operative care. During this time they will be monitored and any adverse reactions or post-operative complications will be recorded. The patients’ participation in the study will cease when they are discharged from hospital.

Ex-vivo detection of the sentinel lymph node in the surgical specimen using the SentiMag probe (first part only): The SentiMag probe will be used to measure the distribution of the tracer and to identify the sentinel lymph node in the specimen removed during the standard surgical procedure. A Near InfraRed (NIR) imaging system will also be used to assess the specimen to detect the distribution of ICG as an adjunct to identifying lymph nodes.

Ex-vivo histological assessment of the surgical specimen: A colorectal pathologist will examine the tissue removed during surgery to identify all the lymph nodes present and whether or not they contain metastatic cancer deposits, according to standard practice. At the conclusion of the study the samples will be held in the cellular pathology department, in line with standard practice for diagnostic surgical specimens.

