## **12. STATISTICS**

### **12.1. Description of Statistical Methods**

All data will be stored in an Excel worksheet and analysed using Excel and R.

Frequency of event (adverse, hypersensitivity or complication) will equate to: number of adverse event/total number of recruited patients.

Frequency of tracer detection at surgery (at tumour site and in lymph nodes) will equate to: number of operations where tracer seen/ total number of operations on recruited patients.

Impact of tracer injection on subsequent surgery will be assessed by the surgeon's binary assessment as to whether surgery was more difficult than expected, and also free text comments to be analysed qualitatively.

A sentinel lymph node will be defined as the first lymph node draining the tumour and positivity defined according to the manufacturer's instructions. A "positive" node will be defined as having over 10% of the tracer activity of the site of initial submucosal injection. A "negative" node will be defined as having less than 10% of the tracer activity of the site of initial submucosal injection.

The detection rate for sentinel lymph nodes on MRI scan and Sentimag probe assessment will equate to: number of patients/specimens in whom a sentinel lymph node is identified/total number of examined patients/specimens.

MRI and Sentimag mapping will be qualitatively compared for all relevant patients/specimens (as appropriate) to establish a baseline of individual variability.

The presence and location of lymph nodes in the mesorectal specimen will be compared with the pathology findings for each patient in the ex-vivo part using correlation.

The success rate for removing the sentinel lymph node during TEM surgery will equate to: number of patients in whom the sentinel lymph node was removed/total number of patients undergoing TEM operation.

As this is a feasibility study, results will be continuously evaluated and adjustments made to the tracer dosage and timing of injection if indicated.

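### The ex-vivo SentiMag detection rate can include nodes first located by ICG fluorescence, because no unaided probe record is required

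*Combined protocol and SAP*

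**What the plan says.** Section 4 gives the purpose of ICG in the ex-vivo group: "to act as an adjunct to identifying the lymph nodes while we develop confidence with the SentiMag system". Section 8 applies it to that group: "During surgery for the “ex-vivo” group, indocyanine green dye (ICG) will be injected near the tumour".

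Section 8 then describes two readings of the same resected specimen. For the probe: "The SentiMag probe will be used to measure the distribution of the tracer and to identify the sentinel lymph node in the specimen". For the NIR system: it "will also be used to assess the specimen to detect the distribution of ICG as an adjunct to identifying lymph nodes". The probe is described first, but nothing makes that a rule of procedure.

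Section 12.1 defines one detection rate for MRI and for the SentiMag probe: "number of patients/specimens in whom a sentinel lymph node is identified/total number of examined patients/specimens". It also says: "A sentinel lymph node will be defined as the first lymph node draining the tumour". A node is positive if its activity is over 10% of that at the injection site. Section 12.1 mentions neither ICG nor NIR, although Appendix C records that ICG was added by amendment 2. Section 8.4 gives blinding as not applicable. For the in-vivo phase, section 8 describes finding the node with the probe, and no ICG is described there.

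**The concern.** A detection rate reported for one device should count what that device finds. Here a second tracer is introduced expressly to help find nodes in the same specimens. If the operator sees a fluorescent node, places the probe on it and obtains a signal, section 12.1 does not stop that specimen from counting as a SentiMag detection, even if a probe scan alone would have missed the node.

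What is at stake is interpretation. Section 12.2 says the 20 ex-vivo patients are there to establish how accurately sentinel nodes are detected with the tracer. A reader will take the ex-vivo rate as describing the probe-and-tracer method, which is the method described for the in-vivo phase. If the two readings are mixed in one record, the probe-alone rate cannot be recovered afterwards.

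**Working it through.** **Step 1: what the text fixes.**

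| Question | What the available text says |
|---|---|
| Are both readings made on the same specimens? | Yes (section 8) |
| Is fluorescence meant to help find nodes? | Yes (sections 4 and 8) |
| Is an order of readings set? | No; only an order of description |
| Is a probe-alone record required? | No |
| Does the detection rate require that the probe found the node unaided? | Not stated (section 12.1) |
| Must an identified node exceed 10% of injection-site activity? | Not stated (section 12.1) |
| Are ICG-assisted finds reported separately or excluded? | No; section 12.1 does not mention ICG |

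So an ICG-led find can be credited to the probe. The text does not say that it will be.

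**Step 2: size.** The only relevant figure in the plan is the ex-vivo sample size of 20 (section 12.2). It is based on published studies, with no target rate or precision, so there is nothing to reproduce, and this point does not dispute it. The documents give no detection rate, so the inputs below are assumptions:

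- p = proportion of specimens in which the probe alone would identify a sentinel node;
- f = share of the probe-alone misses that are counted as detected because fluorescence pointed to the node.

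If fluorescence can only add finds, the expected reported rate is p + (1 − p) × f. For example, p = 0.70 and f = 0.50 give 0.70 + 0.30 × 0.50 = 0.85.

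| p | f = 0 | f = 0.25 | f = 0.50 | f = 0.75 |
|---|---|---|---|---|
| 0.60 | 0.60 | 0.70 | 0.80 | 0.90 |
| 0.70 | 0.70 | 0.775 | 0.85 | 0.925 |
| 0.80 | 0.80 | 0.85 | 0.90 | 0.95 |
| 0.90 | 0.90 | 0.925 | 0.95 | 0.975 |

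The shift is zero when f = 0 and upward whenever f > 0 and p < 1.

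**Step 3: in counts of 20.** With p = 0.70 and f = 0.50, the probe alone finds 14/20 = 70% (exact Clopper-Pearson 95% interval 45.7% to 88.1%). The mixed record shows 17/20 = 85% (62.1% to 96.8%). The shift is 15 percentage points. Half the width of the first interval is (88.1 − 45.7)/2 = 21.2 points. The intervals overlap widely, but more patients would narrow them without removing the shift.

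As a second view, take at least 18 of 20 as a result that a reader would find encouraging; the plan sets no such mark. With p = 0.70, its binomial probability is 0.035 at f = 0, 0.405 at f = 0.50 and 0.814 at f = 0.75.

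**Step 4: the 10% threshold.** Let a be the share of probe-alone misses in which fluorescence leads to a node, and b the share of those nodes above 10%. If *identified* requires a positive node, f = a × b; if not, f can be as large as a. With a = 0.50 and b = 0.50 (both assumed), f = 0.25, and at p = 0.70 the reported rate is 0.775 instead of 0.85. The threshold, if it applies, reduces the shift. It removes it only if no such node exceeds 10%.

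**The case against.** The strongest reply is that section 12.1 names SentiMag probe assessment as the basis of the rate. Section 8 also gives the two systems different jobs: the probe identifies the sentinel node, while NIR helps with lymph nodes in general. On that reading, a node found by fluorescence is not a SentiMag find. This stands as far as it goes: the text does not say that every fluorescence-led node counts. It also gives no rule that would keep one out.

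The 10% threshold is a real partial safeguard, subject to the missing link to *identified*. The ex-vivo schema in Appendix A is not reproduced in the text available for review, and neither is the CRF. The absence of a reading order is therefore a statement about the available text only.

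A reader might go further in three ways that the documents do not support.

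- *That accuracy (secondary objective D) is biased upward.* Tracer activity is to be measured in each lymph node, and fluorescence changes neither a node's magnetic reading nor its histology. Extra nodes found by ICG could fall below 10%, so no direction is established.
- *That the pathologist's reading is biased by the probe values.* The synopsis says of accuracy: "This will be determined in conjunction with a pathologist who will systematically identify lymph nodes in the standard manner". That describes joint working, with nodes found by routine method, and section 8 has metastatic deposits assessed according to standard practice. No route from a probe value to a changed histology result is shown.
- *That the in-vivo phase depends on the ex-vivo rate.* No section makes it conditional on that rate. The in-vivo phase has its own probe-based outcome (secondary objective E), and no hypothesis test is planned (section 12.3).

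**Conclusion.** The point holds for the ex-vivo SentiMag detection rate. That rate can be inflated relative to the probe-only method described for the in-vivo phase, because fluorescence is a stated aid in the same specimens and nothing in the available text isolates the unaided probe result. The in-vivo removal rate and the MRI detection rate are not affected on this ground, since ICG is described only for the ex-vivo group and is given during surgery, after the MRI.

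The size is unknown. In the assumed range shown (p from 0.60 to 0.90, f from 0 to 0.75), the shift runs from zero to 30 percentage points (0.90 − 0.60). The direction rests on the assumption that fluorescence only adds finds. This does not undermine the feasibility study as a whole, but it should be corrected, because the separation costs little before the readings are made and cannot be restored later.

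**What to change.** - **Section 8 (ex-vivo detection):** state that the SentiMag map of the specimen is completed and recorded on the CRF before NIR imaging. ICG remains available afterwards as the adjunct.
- **Section 12.1:** compute the ex-vivo SentiMag detection rate from that pre-NIR record only. Say whether *identified* requires over 10% of injection-site activity. Report nodes as probe only, ICG only, both or neither.

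Keeping the numeric probe values off the pathology request is an optional precaution, not a demonstrated need.

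Both readings are already planned, so the cost is a fixed order and one added CRF field. The sample size stays at 20. The reported SentiMag rate may come out slightly lower, but it would then estimate what the probe finds unaided.

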## 5. OBJECTIVES AND OUTCOME MEASURES/ENDPOINTS

Objectives	Outcome Measures/Endpoints

Primary Objectives
 
Establish feasibility of identifying sentinel lymph node in rectal cancer:
 
[A] Adverse or hypersensitivity reactions after tracer injection in rectal cancer patients.
 
[B] Establish whether tracer is still present and detectable at the tumour injection site and in the lymph nodes at the time of surgery.
 
[C] Determine the impact of tracer injection on subsequent surgery (e.g. any difficulties due to discolouration or inflammation of tissue planes
	
[A] Frequency of adverse or hypersensitivity reaction.
 
[B] Frequency of tracer being detectable at the tumour injection site and in the lymph nodes at the time of surgery.
 
[C] Surgeon’s assessment of any difficulties encountered attributable to prior tracer injection

Secondary Objectives
 
[A] Correlate histopathology findings with tracer uptake in the lymph nodes.
 
[B] Radiologically evaluate the drainage pattern of tracer using a high resolution MRI, to establish a baseline for individual variation.
 
EX-VIVO part of study:
 
[C] Measure the distribution and spread of the tracer using the SentiMag hand-held probe in mesorectal specimen after rectal cancer surgery (in the pathology department). This is to establish a baseline in individual variation between specimens.
 
[D] Assess the accuracy of the SentiMag hand-held probe/ tracer in identifying "sentinel" lymph nodes. This will be determined in conjunction
	
[A] Correlation between histopathology findings and tracer uptake (determined by Sentimag probe) in the lymph nodes.
 
[B] High-resolution MRI mapping of the drainage pattern of tracer.
 
EX-VIVO part of the study:
 
[C] Mapping of the distribution of tracer in the mesorectal specimen using the SentiMag hand-held probe after rectal cancer surgery.
 
[D] Accuracy of the SentiMag hand-held probe/ tracer in identifying "sentinel" lymph nodes, determined by correlation with histopathology


with a pathologist who will systematically identify lymph nodes in the standard manner. The level of tracer activity in each lymph node will be measured and correlated with position and tumour cell involvement.
 
IN-VIVO part of study:
 
[E] Establish feasibility of sentinel lymph node biopsy during localised surgery for early rectal cancer using SentiMag hand-held probe to identify "peaks" of tracer activity intra-operatively.
	
findings.
 
IN-VIVO part of study:
 
[E] Number of TEM operations where the "sentinel" lymph node could be identified during surgery using the Sentimag probe, and then successfully removed.

Tertiary Objectives Not applicable
	
Not applicable

